#### **9.4.9 Multiple Comparison/Multiplicity**

N/A

#### **9.4.10 Tabulation of Individual Response Data**

Individual participant data will be listed by measure and time point.

#### **9.4.11 Exploratory Analyses**

Please see additional subgroup analysis.

### **9.5 Sample Size**

Using a sample of 160 patients, 40 in HBOT arm and 120 in SOC arm (post matching) we can detect a reduction of 22.5% or higher, against the null of no difference, with 80% power at significance level of 0.05, assuming that the mortality rate in SOC arm is about 80%.

For the secondary analysis, our proposed sample of 160 patients will similarly allow us to detect a difference of 22.5% in need for ventilation between HBOT group and SOC group with 80% power. For comparing the continuous outcome of number of days in ventilation, we have 80% power to detect effect size (cohen's d) of 0.51 with 160 patients.

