Objectives	Determine Safety and Efficacy of Hyperbaric Oxygen as an adjunctive treatment for COVID 19 hospitalized patients
Methodology	This is a prospective interventional cohort study that will evaluate the risks and benefits of HBOT utilization for COVID-19 confirmed patients in the hospital setting.
Endpoint	Primary endpoint: Death Secondary endpoints: Need for invasive mechanical ventilation, reduction in days on a ventilator Safety endpoints: Incidence of adverse events (AE) and severe adverse events (SAE)
Study Duration	Approximately two months, but subject to change given the nature of the ongoing pandemic.
Participant Duration	Duration of inpatient hospitalization.
Intervention	Up to 5 hyperbaric oxygen treatments at 2.0 ATA for 90 minutes dependent on the ability of the patient to participate
Population	Patients greater than 18 years of age diagnosed with COVID19 and under respiratory distress.

CONFIDENTIAL

This material is the property of the NYU School of Medicine and Langone Medical Center. Do not disclose or use except as authorized in writing by the study sponsor

Eligibility Criteria	
Inclusion criteria:
 
 
1. Laboratory confirmed COVID-19 positive or a clear clinical diagnosis of COVID-19
 
2. SpO2 <93% after trial of non-rebreather with no less than 85% SpO2
 
3. At least 18 years of age
 
4. No absolute contraindication for Hyperbaric Oxygen
 
 
Exclusion criteria:
 
 
1. Pregnancy
 
2. Untreated Pneumothorax
 

Study Sites	
NYU Winthrop Hospital          NYU Langone School of Medicine          Northwell Hospital          Cleveland Clinic          Loma Linda          Jacobi/Einstein          University of Kentucky Hospital          Westchester Medical Center          Geisinger Commonwealth School of Medicine          Spectrum Health Hospital          University of Illinois at Urbana-Champaign

Number of participants	
40 patients in severe respiratory distress          (SpO2 < 93% on RA, but oxygen responsive)

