#### **4.2.2 Secondary Study Endpoints**

The secondary endpoints will be whether a patient needed invasive mechanical ventilation and the number of days on a ventilator for those who did receive ventilation. The rate of patients who needed mechanical ventilation among those who received hyperbaric oxygen will be compared to the rate in a matched cohort of patients that received standard of care and did not get hyperbaric oxygen.

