### 5.2 Exclusion Criteria

An individual who meets any of the following criteria will be excluded from participation in this study:

1. Pregnancy
2. Untreated Pneumothorax
3. Intubated patients
4. Patients on IV drips

Other conditions are all relative contraindications that need to be discussed with the treating physician and the hyperbaric medicine physician.

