### 9.2 Statistical Hypotheses

For primary endpoint: we hypothesize that the proportion of patients who died in the HBOT group will be lower than that in the SOC group. We will test the hypothesis against the null of no difference in proportions of incident mortality.

For secondary end points:

1. We hypothesize that the proportion of patient who need mechanical ventilation in the HBOT group will be lower than that in the SOC group. We will test the hypothesis against the null of no difference in proportions between the two groups.
2. We further hypothesize that the patients in the HBOT group will spend on average fewer number of days on a ventilator compared to those in the SOC group. We will test the hypothesis against the null that there is no difference in means between the two groups.

Safety analysis: We hypothesize that the rate of any severe adverse effects will be smaller in the HBOT group compared to the SOC group. We will test the hypothesis against the null of no difference.

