### 9.3 Analysis Datasets

We will compare study endpoints and safety outcomes between the 40 patients who received HBOT treatment with a matched comparison group of 120 patients who received standard treatment. Matching will be based on age, gender, comorbidity, and disease severity. The eligibility criteria for the SOC group will be consistent with that of the HBOT group.

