#### **9.4.3 Analysis of the Secondary Endpoint(s)**

The first secondary endpoint is a binary outcome indicating whether a patient needed a mechanical ventilation. We will compute the proportion of patients who needed mechanical ventilation during their treatment for each matched group. The proportion in HBOT arm will be compared with that in matched SOC using chi-square test for proportions. Estimate of difference in proportion along with 95% confidence interval will be reported. Similar to the primary analysis, we will adjust for any potential confounders, deemed important in the baseline analysis, by using multivariable logistic regression. Estimate of odds-ratio and 95% confidence interval will be reported.

To compare the average number of days spent in ventilator between the two groups, we will use linear regression analysis. The distribution of outcome, the number of days in ventilator, will be assessed graphically and by conducting test for normality. If we find the evidence of deviation from normal distribution the outcome will be log transformed before proceeding with analysis. We will also adjust for any potential confounders, deemed important in the baseline analysis. Slope coefficient along with 95% confidence interval will be reported as an estimate of difference between HBOT and SOC groups.

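### Section 9.5 powers ventilator days on all 160 patients, but 4.2.2 counts only ventilated patients; power at d = 0.51 is then about 59% to 70%, not 80%

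*Combined protocol and SAP*

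**What the plan says.** Section 9.5 (Sample Size) ends with a power statement for ventilator days: "we have 80% power to detect effect size (cohen's d) of 0.51 with 160 patients". The 160 are the 40 HBOT and 120 matched SOC patients.

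Other sections bear on who those patients are:

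- Section 4.2.2 defines the endpoint as "the number of days on a ventilator for those who did receive ventilation".
- Section 5.2 lists "Intubated patients" among the exclusions, and section 9.3 says "The eligibility criteria for the SOC group will be consistent with that of the HBOT group". Neither group therefore starts on a ventilator.
- Section 9.4.2 assumes that about 80% of SOC patients will need mechanical ventilation. Section 9.5 adds a detectable difference of 22.5% in need for ventilation.
- The Protocol Summary lists "Need for invasive mechanical ventilation, reduction in days on a ventilator". Section 9.2 hypothesises that "the patients in the HBOT group will spend on average fewer number of days on a ventilator". Section 9.4.3 says "To compare the average number of days spent in ventilator between the two groups, we will use linear regression analysis". None of the three repeats the restriction to ventilated patients, and none says that unventilated patients score 0 days.
- If the distribution is not normal, section 9.4.3 says "the outcome will be log transformed before proceeding with analysis".

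**The concern.** The endpoint definition and the power statement use different denominators. Both can be right only if every patient in both groups goes on to be ventilated, and the plan's own 80% SOC rate rules that out. The number contributing is smaller than 160, and the power lower than stated.

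The choice of who is counted also changes what is estimated: mean days among ventilated patients, or mean days across all patients. Apart from 4.2.2, the sections leave this unsaid. Section 9.1 defers the formal SAP to the end of a non-blinded study, so a question left open now could be settled after the outcomes are known.

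**Working it through.** **Inputs.** Two-sided 0.05 (9.4.1); d = 0.51 and 40 v 120 (9.5); SOC ventilation about 80% (9.4.2); detectable difference in ventilation of 22.5 points (9.5). The plan gives no HBOT ventilation rate, so two scenarios are used.

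**Formula.** Two-sample t-test with groups n1 and n2: noncentrality λ = d × √(n1·n2/(n1+n2)), and power from the noncentral t with n1+n2−2 degrees of freedom. As a rough check, power ≈ Φ(λ − 1.96).

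**Step 1: reproduce the plan's figure.** For 40 v 120, √(4800/160) = √30 = 5.477 and λ = 0.51 × 5.477 = 2.793. Power is 79.3% (79.8% by the normal approximation). The d detectable with 80% power is 0.515 (0.511 normal). The statement in 9.5 is therefore correct arithmetic for all 160 patients. Alternatives do not fit: an 80:80 split gives 89.4%, and a one-sided test gives 87.2%.

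**Step 2: count the contributors under 4.2.2.**

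- SOC: 120 × 0.80 = 96.
- HBOT, no effect on need for ventilation: 40 × 0.80 = 32.
- HBOT, 22.5 points lower: 40 × (0.80 − 0.225) = 40 × 0.575 = 23. This is the plan's detectable alternative, not a rate that it expects.

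**Step 3: recompute at d = 0.51.**

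| Ventilated, HBOT v SOC | √(n1·n2/(n1+n2)) | λ | Power | Detectable d at 80% |
|---|---|---|---|---|
| 40 v 120 (as stated) | √30 = 5.477 | 2.793 | 79.3% | 0.51 |
| 32 v 96 | √24 = 4.899 | 2.498 | 69.8% | 0.58 |
| 23 v 96 | √18.55 = 4.308 | 2.197 | 58.7% | 0.66 |

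Letting the numbers ventilated vary binomially around these expectations gives mean power of 69.7% and 58.3%, so fixing them at their means does not drive the result.

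**Step 4: sensitivity to the ventilation rate.** These rates are assumptions, equal in both groups, and are not in the documents. At 60% ventilated (24 v 72), power is 57.2% and detectable d is 0.67. At 50% (20 v 60), power is 49.6% and detectable d is 0.73.

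**Step 5: the zero-days reading.** If unventilated patients scored 0 days, all 160 would contribute. The expected zeros are 24 SOC + 8 HBOT = 32 of 160 (20%) with no effect on ventilation, or 24 + 17 = 41 of 160 (26%) with the 22.5-point effect. The logarithm of zero is undefined, and 9.4.3 gives no offset.

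**Minor related point.** Section 9.4.2, under the mortality endpoint, attaches the 22.5% calculation to 80% SOC ventilation. Section 9.5 attaches it to 80% SOC mortality and extends it to ventilation. The plan appears to assume about 80% for each, but 9.4.2 gives no mortality rate. Exact power of the uncorrected chi-squared test with 40 v 120 is 79.2% for 80% v 57.5%, and 62.4% for 80% v 62% (a relative reduction: 0.80 × 0.775 = 0.62). Only absolute percentage points reproduce the stated 80%.

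**The case against.** The arithmetic in 9.5 is right for the number it names. The plan assumes a ventilation rate for SOC only, so both HBOT counts are scenarios, and the 23 borrows a detectable difference from another endpoint. Section 4.2.2 is explicit, and silence in later sections does not contradict it. The log-of-zero difficulty arises only under a reading that 4.2.2 rules out, and 9.4.1 speaks of considering suitable transformations more generally. The plan names no SD or target in days, so 0.51 is simply what 160 patients can detect, and a d computed with zeros included is not the same quantity as a d among ventilated patients. Finally, this is one secondary endpoint of a non-randomised pilot cohort, and no decision rule depends on the figure.

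Most of this stands as a limit on scope. The HBOT counts must be read as scenarios, the log problem belongs to the zero-days reading alone, and the primary calculation is untouched. None of it reconciles 9.5 with 4.2.2. Even if all 40 HBOT patients were ventilated, the plan's SOC rate would leave 24 of the 120 SOC patients without a value.

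**Conclusion.** The concern holds. Under the endpoint's definition in 4.2.2 and the plan's 80% SOC ventilation rate, power at d = 0.51 is 69.8% if HBOT does not change the need for ventilation, and 58.7% if it lowers it by 22.5 points. That is about 10 to 21 points below the stated 80%. These figures assume a two-sample t comparison at two-sided 0.05 without covariate adjustment, and they fall further if fewer patients are ventilated. The fault is the denominator, not the calculation. The zero-days reading would rescue the denominator only by changing the endpoint, and the prescribed log transform could not then be applied as written. The plan should be corrected, though this affects only the stated precision and definition of one secondary endpoint.

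**What to change.** **1. Say who contributes ventilator days, in the same words in 4.2.2, 9.2 and 9.4.3.** Then take one of two routes:

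- *Ventilated patients only.* Restate 9.5 on the expected number ventilated and name the rates assumed. For example: with 80% ventilated in both groups (32 HBOT, 96 SOC), power at d = 0.51 is about 70%, and 80% power is reached at d = 0.58; with 57.5% ventilated in the HBOT group (23), the figures are about 59% and d = 0.66. Recompute if another rate is adopted.
- *Unventilated patients count as 0 days.* Keep 160, amend 4.2.2, and replace the log transform in 9.4.3 with a method that allows zeros. Make clear in 9.5 that d then refers to the distribution with zeros included.

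**2. Minor.** Reconcile 9.4.2 with 9.5 by stating the assumed SOC mortality and SOC ventilation rates separately, and say that 22.5% means absolute percentage points.

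**Cost.** Wording in 4.2.2, 9.2, 9.4.2, 9.4.3 and 9.5. The first route leaves a less favourable power figure for one secondary endpoint. The second changes the endpoint definition and the analysis method. Neither needs extra patients or new data.

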### **9.6 Measures to Minimize Bias**

#### **9.6.1 Enrollment/Randomization/Masking Procedures**

There will be no randomization in this study. Considering the urgency of the current pandemic, it does not seem appropriate to consent a patient and then not offer them the intervention. We are also only collecting SOC data and there is a very high volume of patients, so large numbers of patients meeting criteria will be

CONFIDENTIAL

This material is the property of the NYU School of Medicine and Langone Medical Center. Do not disclose or use except as authorized in writing by the study sponsor

Interventional Template Version: 11 January 2019

available for chart review for the comparison group. Any patients who might be randomized to SOC would not have any study-related activity other than collection of SOC data in the EMR.

### **9.6.2 Evaluation of Success of Blinding**

N/A

### **9.6.3 Breaking the Study Blind/Participant Code**

N/A

## **10 Source Documents and Access to Source Data/Documents**

The study case report form (CRF) is the primary data collection instrument for the study. All data requested on the CRF must be recorded. All missing data must be explained. If a space on the CRF is left blank because the procedure was not done or the question was not asked, write "N/D". If the item is not applicable to the individual case, write "N/A". All entries should be printed legibly in black ink. If any entry error has been made, to correct such an error, draw a single straight line through the incorrect entry and enter the correct data above it. All such changes must be initialed and dated. DO NOT ERASE OR WHITE OUT ERRORS. For clarification of illegible or uncertain entries, print the clarification above the item, then initial and date it.

Access to study records will be limited to IRB-approved members of the study team. The investigator will permit study-related monitoring, audits, and inspections by the IRB/EC, government regulatory bodies, and University compliance and quality assurance groups of all study related documents (e.g. source documents, regulatory documents, data collection instruments, study data etc.).

Participation as an investigator in this study implies acceptance of potential inspection by government regulatory authorities and applicable University compliance and quality assurance offices.

## **11 Quality Assurance and Quality Control**

QC procedures will be implemented beginning with the data entry system and data QC checks that will be run on the database will be generated. Any missing data or data anomalies will be communicated to the site(s) for clarification/resolution.

Study coordinators will verify that the clinical trial is conducted and data are generated, documented (recorded), and reported in compliance with the protocol, GCP, and the applicable regulatory requirements (e.g., Good Laboratory Practices (GLP), Good Manufacturing Practices (GMP)).

The investigational site will provide direct access to all trial related sites, source data/documents, and reports for the purpose inspection by local and regulatory authorities.

## **12 Ethics/Protection of Human Subjects**

### **12.1 Ethical Standard**

The investigator will ensure that this study is conducted in full conformity with Regulations for the Protection of Human Subjects of Research codified in 45 CFR Part 46, 21 CFR Part 50, 21 CFR Part 56, and/or the ICH E6.

### **12.2 Institutional Review Board**

The protocol, informed consent form(s), recruitment materials, and all participant materials will be submitted to the IRB for review and approval. Approval of both the protocol and the consent form must be obtained before any participant is enrolled. Any amendment to the protocol will require review and approval by the IRB before the changes are implemented to the study. All changes to the consent form

CONFIDENTIAL

This material is the property of the NYU School of Medicine and Langone Medical Center. Do not disclose or use except as authorized in writing by the study sponsor  
Interventional Template Version: 11 January 2019

will be IRB approved; a determination will be made regarding whether previously consented participants need to be re-consented.

### **12.3 Informed Consent Process**

#### **12.3.1 Consent/Accent and Other Informational Documents Provided to Participants**

Consent forms describing in detail the study device, study procedures, and risks are given to the participant or the participant's legally authorized representative and written documentation of informed consent is required prior to starting intervention/administering study product. A consent form is submitted with this protocol.

### **12.4 Consent Procedures and Documentation**

Informed consent is a process that is initiated prior to the individual's agreeing to participate in the study and continues throughout the individual's study participation. Informed consent will be obtained by a member of the research team. Patients in the emergency room or other inpatient unit who have tested positive for COVID-19 or have a clear clinical diagnosis of COVID-19 and who are in respiratory distress will be approached for consent. Extensive discussion of risks and possible benefits of participation will be provided to the participants and their families. Consent forms will be IRB-approved and the participant or their legally authorized representative will be asked to read and review the document. The investigator will explain the research study to the participant and answer any questions that may arise. All participants will receive a verbal explanation in terms suited to their comprehension of the purposes, procedures, and potential risks of the study and of their rights as research participants. Participants will have the opportunity to carefully review the written consent form and ask questions prior to signing. The participants should have the opportunity to discuss the study with their surrogates or think about it prior to agreeing to participate.

In order to confirm that the participant is capable of providing informed consent, the hyperbaric oxygen physician will ask the patient to reiterate the information given to them.

The participant will sign the informed consent document prior to any procedures being done specifically for the study. The participants may withdraw consent at any time throughout the course of the trial. A copy of the signed informed consent document will be given to the participants for their records. The rights and welfare of the participants will be protected by emphasizing to them that the quality of their medical care will not be adversely affected if they decline to participate in this study.

A copy of the signed informed consent document will be stored in the subject's research record. The consent process, including the name of the individual obtaining consent, will be thoroughly documented in the subject's research record. Any alteration to the standard consent process (e.g. use of a translator, consent from a legally authorized representative, consent document presented orally, etc.) and the justification for such alteration will likewise be documented.

EPIC will be used to determine if subjects meet study eligibility criteria as well as to determine if they have a legally authorized representative. If the legally authorized representative is not noted in the subject's medical record, we would follow New York State's hierarchy:

- A court-appointed Legally Authorized Representative/guardian or a guardian authorized to decide about health care pursuant to Article 81 of the Mental Hygiene Law.
- An individual who is designated as a representative/agent through a health care proxy signed by both the subject and the appointed representative/agent. For a health care proxy to be effective, it must have been signed at a time when the subject had decision-making capacity. In addition, the health care proxy must not specifically prohibit research.
- The spouse, if not legally separated from the subject, or domestic partner.
- A son or daughter 18 years of age or older.
- A parent.
- A sibling 18 years of age older.

CONFIDENTIAL

This material is the property of the NYU School of Medicine and Langone Medical Center. Do not disclose or use except as authorized in writing by the study sponsor

- A step-child, step-sibling, step-parent, grandparent or grandchild 18 years of age or older who has maintained such regular contact with the subject as to be familiar with the subject's activities, health or beliefs.

Subjects will be regularly assessed throughout the study to determine whether or not they have regained or lost the capacity to consent. If subjects who have the capacity to consent at the onset of the study lose capacity during the study, their legally authorized representative will be identified and consent sought for the subject's continued participation in the study. If subjects regain the capacity to consent during the study and decline to continue participation, they will be asked if previously collected data can still be used. If they decline, this data will be discarded.

## **12.5 Posting of Clinical Trial Consent Form**

N/A

## **12.6 Participant and Data Confidentiality**

Information about study subjects will be kept confidential and managed according to the requirements of the Health Insurance Portability and Accountability Act of 1996 (HIPAA). Those regulations require a signed subject authorization informing the subject of the following:

- What protected health information (PHI) will be collected from subjects in this study
- Who will have access to that information and why
- Who will use or disclose that information
- The rights of a research subject to revoke their authorization for use of their PHI.

In the event that a subject revokes authorization to collect or use PHI, the investigator, by regulation, retains the ability to use all information collected prior to the revocation of subject authorization. For subjects that have revoked authorization to collect or use PHI, attempts should be made to obtain permission to collect at least vital status (i.e. that the subject is alive) at the end of their scheduled study period.

Participant confidentiality is strictly held in trust by the participating investigators, their staff, and the sponsor(s) and their agents. This confidentiality is extended to cover testing of biological samples in addition to the clinical information relating to participants. Therefore, the study protocol, documentation, data, and all other information generated will be held in strict confidence. No information concerning the study or the data will be released to any unauthorized third party without prior written approval of the sponsor.

The study monitor, other authorized representatives of the sponsor, representatives of the IRB or pharmaceutical company supplying study product may inspect all documents and records required to be maintained by the investigator, including but not limited to, medical records (office, clinic, or hospital) and pharmacy records for the participants in this study. The clinical study site will permit access to such records.

The study participant's contact information will be securely stored at each clinical site for internal use during the study. At the end of the study, all records will continue to be kept in a secure location for as long a period as dictated by local IRB and Institutional regulations.

Study participant research data, which is for purposes of statistical analysis and scientific reporting, will be transmitted to and stored at NYU Langone Medical Center. This will not include the participant's contact or identifying information. Rather, individual participants and their research data will be identified by a unique study identification number. The study data entry and study management systems used by clinical sites and by NYU Langone Medical Center research staff will be secured and password protected. At the end of the study, all study databases will be de-identified and archived at the NYU Langone Medical Center.

CONFIDENTIAL

This material is the property of the NYU School of Medicine and Langone Medical Center. Do not disclose or use except as authorized in writing by the study sponsor

Interventional Template Version: 11 January 2019

